- Concurrent severe depression defined by a score greater than 29 on the Beck Depression Inventory (BDI-II)
- Prior intracerebral surgical intervention for PD, including deep brain stimulation, lesional surgery, growth factor administration, gene therapy, or cell transplant
- Already actively participating in a trial of a device, drug, or surgical treatment for PD, or trial participation within 30 days prior to the baseline visit
- Diagnosis of diabetes mellitus of any type, established historically or by:
 - Fasting plasma glucose levels equal or above 126 mg/dl
 - Hemoglobin A1c equal or above 6.5%
- Active treatment with oral antidiabetic medications
- History of severe cardiac disease (e.g., angina, myocardial infarction, or cardiac surgery) in the preceding year
- Significant systemic illness likely to result in deterioration of the patient's condition or, in the Investigator’s opinion, affect the patient's safety during the study, including in particular:
 - 1) History of pancreatitis
 - 2) Personal or family history of medullary thyroid carcinoma
 - 3) History of multiple endocrine neoplasia syndrome type 2
 - 4) History of alcoholism
 - 5) Severe gastrointestinal disease, including gastroparesis
 - 6) Treatment with immunosuppressive medications (e.g., systemic corticosteroids) within the last 90 days or chemotherapeutic agents for malignancy within the last 2 years
 - 7) Severe renal insufficiency (CrCl <30)
 - 8) Moderate or severe hepatic impairment
 - 9) Severe hypertriglyceridemia (triglycerides >500 mg/dl)
 - 10) Body mass index <18.5
- Females who are pregnant or breast feeding
- Prior serious hypersensitivity reaction to Victoza or any of the product components

Withdrawal Criteria: In the absence of a medical contraindication or significant protocol violation,

every effort will be made by the Principal Investigator (PI) to keep accepted subjects in the study. However, should the subject decide to discontinue treatment, all efforts will be made to complete and report the observations as thoroughly as possible, including a complete final evaluation at the time of the subject's withdrawal with an explanation of why the subject is withdrawing from the study. All subjects who prematurely withdraw from the study will receive a follow-up telephone call one month after discontinuation. Study treatment will be stopped if any of the following events occur:

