- The subject has any clinical AE, laboratory abnormality, intercurrent illness, or other medical condition that indicates to the PI that continued participation is not in the best interest of the subject or if it requires the subject to stop taking levodopa or other medications essential to the treatment of Parkinson's disease. Subjects experiencing AEs that are present at the end of their participation in the study should receive follow-up, as appropriate. If possible, the outcome of any AE resulting in withdrawal from the study or that was present at the end of the study will be followed until resolution or return to baseline condition, particularly if the AE was considered by the PI to be related to the study drug;
- The subject requires a concomitant medication that is prohibited in the study;
- The subject wishes to withdraw consent from the study in the absence of a medical need to withdraw, as determined by the Investigator;
- The PI concludes that it is in the best interest of the subject to discontinue study treatment;
- The subject is noncompliant; or
- If pregnancy is suspected while the subject is receiving study treatment, the study medication must immediately be withheld until the result of pregnancy testing is known. If pregnancy is confirmed, the study medication will be permanently discontinued and the subject withdrawn from the study. Reasonable attempts will be made to follow the pregnancy to conclusion in order to obtain information regarding the outcome.

The PI must complete all applicable final visit procedures (e.g., safety laboratory parameters, ECG, physical examination, vital signs [including orthostatic BP and HR]) and study documentation for subjects who withdraw from the study treatment and specify the reason for their withdrawal. Once subjects withdraw from the study, they will revert to the care of their usual physician for treatment/management of their disease as appropriate.

Subject Replacement: A subject who withdraws from the study may not reenter the study.

Rationale for Study Population: (see Background and Significance)

Visit Procedures: (see Study Schedule)

Assessments for Efficacy: The efficacy of liraglutide will be assessed by measures of the drug's effects versus placebo on PD motor and non-motor symptoms quantified on the following scales after study medication titration in active and placebo groups:

- MDS-UPDRS part I, II, III and IV changes from ON medication baseline at 28 and 54 weeks

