Note: While the validity of HOMA-IR as a surrogate measure of peripheral insulin sensitivity has been questioned given its failure to correlate with diet-induced insulin sensitivity in dogs⁶³ and its erroneous prediction of differences in insulin sensitivity between non-diabetic African and European Americans,⁶⁴ virtually all clinical studies report a significant correlation of HOMA-IR (or the similarly derived QUICKI index) with insulin sensitivity directly measured with the euglycemic-hyperinsulinemic clamp technique in normal, prediabetic, and diabetic cases of various ethnicities.⁶⁵⁻⁷⁴ Indeed, the only contrary studies are two reporting that HOMA-IR and/or QUICKI are not correlated with insulin sensitivity in normal Afro-Caribbean adults⁷⁵ and a small population of normal Caucasians.⁷³ Given the body of predictive evidence and to avoid the added expense of oral glucose tolerance tests, the HOMA-IR and QUICKI have been chosen as surrogate measures of peripheral insulin resistance.

In addition, measures of insulin sensitivity in neuronal-origin enriched plasma EVs will be used to test the association of changes in such sensitivity to changes in MDS-UPDRS and MDRS-2 scores from baseline to 28 and 54 weeks. For that purpose, plasma samples will be collected and stored and -80°C to allow for isolation of neuronal origin EVs at the completion of the study.

Subject Compliance: The PI is required to ensure that subjects comply with the drug schedule specified by the study protocol.

Subjects who fail to comply with the drug schedule for 70% of the days since the previous study visit on one occasion will be considered for termination. If the non-compliance was unrelated to an adverse event related to the study drug, then the Investigator will need to evaluate whether the non-compliance is likely to recur. Subjects judged to be high risks for continued non-compliance will be terminated at the discretion of the principal investigator. Subjects who fail to comply with the drug schedule for 70% of the days preceding a study visit on a second occasion must be terminated from the study. This mandatory termination due to non-compliance will be reported on the end of study eCRF unless the non-compliance was attributable to adverse effects of study drug.

STATISTICAL CONSIDERATIONS:

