The last UPDRS, NMSS, and MDRS-2 scores prior to first drug administration will be used as the baseline value in the model and to calculate change from baseline clinical scores. To calculate the change from baseline at week 54, the clinical scores at week 54 will be used. Missing values will be imputed using the last observation carried forward (LOCF) method, including clinical scores on the discontinuation visit. Baseline values will not be carried forward. This methodology will be applied to all treatment groups (liraglutide and placebo).

The assumptions of normality and homogeneity of variance will be explored using probability and residual plots. Data will be tested for normality using the Shapiro-Wilk test. If any of the assumptions are found to be violated, an appropriate transformation of the data or non-parametric test will be considered.

Sensitivity analyses of the primary efficacy endpoint will be performed on the PP population using the same methods described for the FAS population. Summaries of clinical scores, including the change from baseline, will be presented at each visit (i.e., baseline, Week 28, and Week 54). No adjustments have been made to the Type I error rate for the multiple comparisons of the primary or secondary endpoints since this is a phase II study; therefore, results should be interpreted appropriately. No statistical testing within treatment groups will be performed.

Inferential Statistics on Secondary Efficacy Parameter(s): Analyses of secondary efficacy endpoints will be conducted on the FAS and PP populations. The following secondary efficacy endpoints will be analyzed using an approach similar to that described for the primary efficacy endpoints:

- Change in PDQ-39 scores for each domain and total score between baseline and week 54.
- Change in Delis-Kaplan Executive Function System (DKEFS) between baseline and week

- Change in Geriatric Depression Scale between baseline and week 54
- Change in Parkinson's Anxiety Scale scores between baseline and week 54

The safety outcomes of this study will be the following:

- Adverse events
- Serious adverse events
- Clinical laboratory parameters
- Geriatric Depression Scale
- Vital signs
- Physical examination.
- 12-lead ECGs

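### A second compliance failure ends study participation in one section but only study treatment in another; the 70% trigger has two cut-offs, and no Week 54 score is then collected

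*Combined protocol and SAP*

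**What the plan says.** **Subject Compliance.** The first-occasion trigger reads "Subjects who fail to comply with the drug schedule for 70% of the days since the previous study visit on one occasion"; such a subject is considered for termination, and the investigator judges whether the problem is likely to recur. A second occasion leaves no discretion: "Subjects who fail to comply with the drug schedule for 70% of the days preceding a study visit on a second occasion must be terminated", and the sentence ends by naming the study as what they leave. Adverse effects appear in the second-occasion rule only as a reporting exception: the termination "will be reported on the end of study eCRF unless the non-compliance was attributable to adverse effects of study drug".

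**Withdrawal Criteria.** The list of triggers is introduced by "Study treatment will be stopped if any of the following events occur", and one entry is "The subject is noncompliant; or". No percentage is attached. The section asks for a full final evaluation when a subject decides to discontinue, and for one telephone call a month after premature withdrawal. For subjects who withdraw from study treatment it also requires final visit procedures, and the examples given are all safety items. Subjects who withdraw from the study return to their usual physician, and Subject Replacement bars re-entry.

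**Analysis.** Under Statistical Methods, the FAS is the primary efficacy population and is analysed as randomised. It requires at least one post-baseline efficacy score, naming MDRS-2 and MDS-UPDRS. The section on the primary efficacy parameters says "Missing values will be imputed using the last observation carried forward (LOCF) method", including scores from a discontinuation visit, and does not allow baseline values to be carried forward.

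**The concern.** Stopping the drug and stopping observation are different acts. The first leaves room for an observed Week 54 score; the second does not. Here the same event, noncompliance, leads to one act in one section and to the other in another section. Where the stricter text is followed, the plan itself creates a missing outcome that could have been observed.

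Who is affected is also unclear, because the 70% phrase does not say whether it counts days missed or days taken. The reading chosen feeds into the completer count that Assessments for Safety uses to establish tolerability, and into the dropout rate that can trigger extra enrolment under Sample Size Calculation.

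At stake is the FAS comparison at Week 54 in a trial of 57 subjects, only 19 of them on placebo. If noncompliance follows poor tolerability, the replaced or absent scores need not be balanced between arms.

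**Working it through.** **1. The two rules side by side**

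| | Withdrawal Criteria | Subject Compliance, second occasion |
|---|---|---|
| Trigger | noncompliance, no threshold | 70% of days, second time |
| Discretion | none stated | none; mandatory |
| What ends | study treatment | study participation |
| Adverse-effect exception | none stated | eCRF reporting only |

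Nothing in the document says which governs.

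**2. The 70% cut-offs**

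The intervals are nominal days between compliance reviews in the Schedule of events (visit windows ignored, Week 2 taken as day 15). For an interval of L days with m missed days:

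- Reading A, doses taken on fewer than 70% of days: L − m < 0.70L, so m > 0.30L.
- Reading B, doses missed on 70% of days: m ≥ 0.70L.

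| Review visit | L | 0.30L | A: missed days, at least | 0.70L | B: missed days, at least |
|---|---|---|---|---|---|
| Weeks 1 and 2 | 7 | 2.1 | 3 | 4.9 | 5 |
| Week 6 | 27 | 8.1 | 9 | 18.9 | 19 |
| Week 14 | 56 | 16.8 | 17 | 39.2 | 40 |
| Weeks 28 and 54 | 98 | 29.4 | 30 | 68.6 | 69 |
| Week 40 | 84 | 25.2 | 26 | 58.8 | 59 |

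Check for L = 98: with 30 missed days, 68/98 = 69.4% were taken, which triggers A. With 29 missed, 69/98 = 70.4% were taken, which does not. The readings disagree for 30 to 68 missed days in a 98-day interval; other intervals have their own ranges. Everyone caught by B is also caught by A.

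**3. What score exists when the rule fires**

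On-treatment efficacy visits are baseline, Week 28 and Week 54. Compliance is reviewed from Week 1, so a second failure can occur as early as Week 2.

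- Second failure at Week 2, 6 or 14: no scheduled post-baseline efficacy score exists. FAS entry depends on whether the final evaluation includes MDRS-2 and MDS-UPDRS. If it does not, baseline cannot be carried forward and the subject drops out of the FAS.
- At Week 28: the efficacy scores are due at that visit. They stand in for Week 54, which is 54 − 28 = 26 weeks later.
- At Week 40: a discontinuation score stands in from 14 weeks earlier, or the Week 28 score from 26 weeks earlier.
- At Week 54: nothing is missing.

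**4. What a carried-forward score can miss**

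This is an illustration only; it assumes that the means in the protocol's Table 1 apply here. Mean MDRS-2 in the conventionally treated group went from 138.2 at 6 months to 136.6 at 12 months, a change of −1.6. In the exenatide group it went from 142.4 to 142.3, a change of −0.1. Carrying forward a 6-month score would omit 1.6 points of decline for a placebo subject, moving the placebo mean by 1.6/19 = 0.08 points per such subject against the planned difference of 5.1. For a drug-arm subject, a carried on-drug score could instead hide change after the drug was stopped, and the document has no data on that for this trial. The two effects can pull in opposite directions. With no noncompliance rate for either arm, no net bias can be calculated.

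**The case against.** Much can be said for the plan, and most of it stands against stronger readings.

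- A reader might infer that the 70% wording has two opposite meanings. It does not. Both readings act on low compliance and are nested; they are a looser and a stricter cut-off.
- A reader might see a clash with the aim that "every effort will be made by the Principal Investigator (PI) to keep accepted subjects in the study". That sentence opens by excepting significant protocol violations, and repeated failure of the drug schedule may fall within the exception. The conflict that stands is treatment against study.
- A reader might infer that outcomes are simply lost. A final evaluation is foreseen, its listed safety items are examples rather than a full list, and discontinuation scores are used. A subject with such scores stays in the FAS as randomised, so the primary analysis does not thereby become a per-protocol one.
- A reader might infer that subjects leave for a treatment-related reason. The rule applies to both blinded arms and to any cause. Precautions/Over-dosage expects nausea in 5-40% and diarrhea in 17%, which makes unequal loss credible but does not show it.
- LOCF applies to every dropout, and whether off-drug data belong in a phase II estimate is a legitimate choice.

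These points narrow the concern without removing it. The mandatory rule still ends observation, no section plans a Week 54 assessment for these subjects, and the two sections still differ.

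**Conclusion.** The point holds in a limited form. Subject Compliance and Withdrawal Criteria give different consequences for noncompliance and must be reconciled. The trigger has two nested cut-offs that differ more than twofold over 98 days (30 against 69 missed days). A terminated subject has an earlier score in place of Week 54 or, if terminated before Week 28 without both scales, may not be in the FAS.

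That the missingness depends on treatment is plausible, not shown. The number of subjects affected and the bias are unknown, because the plan gives no noncompliance rates. The cut-offs rest on nominal visit days. The wording ambiguity alone would be a matter of missing detail; what makes the point worth acting on is that observable outcomes are replaced by LOCF in an analysis meant to be as randomised, and that avoiding this is cheap.

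**What to change.** 1. Reconcile Subject Compliance with Withdrawal Criteria so that one text says what noncompliance ends. State the trigger once, as a share of scheduled doses taken over a defined interval. The threshold, and when drug is stopped, are for the sponsor to decide.
2. Separate the data rule from the drug rule. Subjects whose study drug is stopped for noncompliance, and who have not withdrawn consent, are still asked to attend the scheduled Week 28 and Week 54 efficacy assessments.
3. Use those observed scores in the FAS analysis in place of LOCF, and keep the PP analysis as the sensitivity analysis.

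The cost is protocol wording and a few extra visits. The downside is some off-drug data in the primary estimate, which should then be described as including outcomes after drug was stopped.

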Study Type: This is a phase II, randomized, double-blinded, placebo-controlled clinical trial.

STUDY POPULATION:

Cases: Fifty-seven patients with a diagnosis of idiopathic PD will be recruited and randomized to receive once daily self-administered injections of liraglutide (1.2 or 1.8 mg, as tolerated) or placebo at the same dose range in a 2:1 study design.

Inclusion Criteria:

- Diagnosis of idiopathic PD according to the United Kingdom Parkinson's Disease Society Brain Bank (UKPDSBB) criteria^a for at least 2 years, and/or a DaT-confirmed diagnosis of PD
- Responsive to levodopa or dopaminergic treatment
- Male or female between 25 and 85 years of age at time of enrollment
 - Women of child-bearing potential (WOCBP) must agree to use a reliable method of contraception (e.g., oral contraceptive or long-term injectable or implantable hormonal contraceptive, double barrier methods (such as condom plus diaphragm, condom plus spermicide foam, condom plus sponge), or intra-uterine devices) throughout the duration of the trial period and must have a negative serum pregnancy test at screening
 - Male patients with female partners who have child bearing potential must agree to use adequate contraception throughout the duration of the trial period

- Capacity to give informed consent
- Ability to self-administer, or to arrange a care partner to administer trial drug, to comply with trial protocol, and to attend necessary clinic visits off medication

a: Note: the study team will not consider the UKPDSBB criterion “more than one affected relative” as exclusionary. According to the scientific community, family history is not regarded as exclusionary and this specific criterion is no longer used (reference).

Exclusion Criteria:

- Diagnosis or suspicion of other causes for Parkinsonism, including drug- or toxin-induced parkinsonism and other neurodegenerative conditions, including multiple system atrophy, progressive supranuclear palsy, Huntington's disease, Wilson's disease, or Alzheimer's disease
- Active treatment with anticholinergic medications (e.g., trixyphenidil or tricyclic antidepressants)
- Known abnormality on CT or MRI brain imaging considered to cause symptoms or signs of neurological dysfunction, or considered likely to compromise compliance with trial protocol
- Concurrent dementia defined by a score lower than 120 on the MDRS-2 and/or inability to complete scale per neuropsychologist’s discretion

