Sample Size Calculation: This is a randomized, double-blinded, placebo-controlled clinical trial that aims to evaluate the effects of liraglutide on motor and non-motor symptoms in patients diagnosed with PD. The primary outcome of this study will be the difference in MDRS-2 scores at baseline and follow-up (52 weeks after titration) between the active and placebo control group. The power analysis was performed utilizing data reported in a previous study using a similar GLP-1 agonist (**Table 1**). While score changes associated with active medication were not compared to a placebo group but to a cohort of patients treated with “conventional PD medication”, this data represent the closest approximation available for power analysis and sample size calculation.

With a total of 57 patients (38 in the drug group and 19 in the placebo group), the study will have an 82.7% chance of rejecting the null hypothesis of equal means, assuming an average critical difference of 5.1 points on the MDRS-2 and a standard deviation of 6.4 for the drug group and 5.3 for the placebo group with a significance level (alpha) of 0.050 using a two-sided two-sample unequal-variance t-test.

This sample allows for a 12% dropout of up to 6 subjects (e.g., if they are diagnosed with T2D during the course of the study) and still maintain 81.3% power with a total of 51 patients (i.e., 36 cases in the drug group and 15 cases in the placebo group). If the rate of drop out is higher than anticipated, the study will enroll and randomize additional subjects; subjects will be enrolled/randomized in multiples of 3 subjects in order to maintain the 2:1 randomization. The additional enrolled subjects will aim to maintain the power of the study. In total, up to 63 patients will be enrolled and randomized. No more than 42 patients, including drop outs, will be exposed to the drug during the trial.

Statistical Methods: The analysis populations for this study are defined as:

1. Full Analysis Set (FAS): all randomized subjects who receive at least one dose of study drug and have a baseline and at least one post-baseline efficacy score (MDRS-2 and MDS-UPDRS).
2. Per-Protocol (PP) population: a subset of the FAS population, excluding subjects with major deviations from the protocol that may substantially affect the results of the primary efficacy analysis.
3. Safety population: all randomized subjects who receive at least one dose of study drug.

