The final determination of protocol violations, and therefore the composition of the PP population, will be made prior to unblinding the database and will be documented separately. Analysis of all efficacy

Table 1 (from Aviles-Olmos et al., 2013⁵¹)

Changes in the score on LED, dyskinesia rating scale, Mattis DRS-2, MADRS, and PDQ39 summary index between baseline and month 14

	Baseline	6 months	12 months	Difference, baseline to 12 months	14 months	Difference, baseline to 14 months
	Mean (SD)	Mean (SD)	Mean (SD)	Mean (SD); 95% CI	Mean (SD)	Mean (SD); 95% CI
LED						
Exenatide	973 (454)	1011 (518)	997 (446)	24.3 (123.6); -37, 78	1015 (467)	42.3 (137); -22, 107
Conventional PD medication	977 (493)	1061 (613)	1121 (620)	143.7 (223.6); 49, 238	1125 (638)	148.0 (232); 50, 246
Dyskinesia rating scale, on medication						
Exenatide	2.3 (2.8)	2.5 (4.1)	3.3 (4.5)	1.0 (4.2); -1.0, 3.0	3.2 (4.0)	1.0 (3.8); -0.8, 2.7
Conventional PD medication	2.6 (2.9)	3.5 (3.9)	2.5 (2.7)	-0.04 (2.7); -1.2, 1.1	2.7 (3.5)	0.1 (4.3); -1.7, 1.9
MATTIS DRS-2						
Exenatide	140.1 (7.7)	142.4 (2.3)	142.3 (2.5)	2.2 (6.4); -0.8, 5.2	142.9 (2.0)	2.8 (6.0); -0.1, 5.6
Conventional PD medication	139.5 (4.5)	138.2 (5.1)	136.6 (6.1)	-2.8 (5.3); -0.6, -5.0	135.9 (8.5)	-3.5 (5.8); -1.1, -6.0
MADRS						
Exenatide	10.9 (5.1)	8.6 (4.2)	9.0 (4.5)	-1.9 (4.6); -4.1, 0.3	10.2 (6.7)	-0.7 (5.9); -3.5, 2.1
Conventional PD medication	11.0 (5.4)	11.3 (6.5)	11.4 (5.6)	0.5 (4.5); -1.4, 2.4	12.4 (5.6)	1.5 (4.7); -0.5, 3.4
PDQ39 summary index						
Exenatide	19.2 (13.5)	18.1 (13.4)	19.6 (13.0)	0.4 (11.4); -4.9, 5.7	21.5 (19.6)	2.3 (11.6); -3.1, 7.7
Conventional PD medication	24.5 (12.8)	25.2 (15.8)	24.0 (15.3)	-0.6 (11.2); -5.3, 4.2	23.4 (16.0)	-1.2 (9.1); -5.0, 2.7

variables will be performed on the FAS and PP population. The FAS population will serve as the primary population for the analysis of efficacy data. Analyses based on the PP population will be considered as a sensitivity analysis. Subjects will be analyzed for efficacy according to the treatment to which they were randomized.

All safety outcomes will be analyzed using the Safety population. Subjects will be analyzed for safety according to the treatment they actually received.

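### The 82.7% power stated for 38 versus 19 patients does not follow from the plan's own inputs, which give 87.6%, and it conflicts with the 81.3% stated for 36 versus 15; the expected completion count also does not match its percentage

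*Combined protocol and SAP*

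**What the plan says.** All the power statements are in the Sample Size Calculation under Statistical Considerations. The planned size is set under Study Population: "Fifty-seven patients with a diagnosis of idiopathic PD will be recruited and randomized", in a 2:1 ratio, which the sample-size text splits as 38 drug and 19 placebo.

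For that size the plan states that "the study will have an 82.7% chance of rejecting the null hypothesis of equal means". The effect is a 5.1-point difference in MDRS-2 change. The spread is given as "a standard deviation of 6.4 for the drug group and 5.3 for the placebo group". Alpha is 0.050, two-sided, and the test is the unequal-variance two-sample t-test.

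On losses it says: "This sample allows for a 12% dropout of up to 6 subjects". Power in that case is put at 81.3%, for 51 patients split as 36 drug and 15 placebo.

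The SDs come from Table 1, in the Mattis DRS-2 rows for change from baseline to 12 months. The exenatide entry is "2.2 (6.4); -0.8, 5.2". The conventional-medication entry, with a minus sign in front, is "2.8 (5.3); -0.6, -5.0".

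Assessments for Safety also gives an expected completion rate above 80%, with 43 subjects in brackets as the matching count. It names no denominator.

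**The concern.** The two power figures look too close together. Going from 38/19 to 36/15 removes six patients, four of them from the smaller arm, which contributes most to the standard error. A fall of only 1.4 points (82.7% to 81.3%) is implausible for that change, so at least one figure is suspect.

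If the 57-patient figure is wrong, the sample-size statement cannot be reproduced from its own inputs and it hides how sensitive power is to losses. That matters because the plan allows randomization to go up to 63 when dropout exceeds expectation, with the aim of maintaining power. If instead the 51-patient figure is wrong, the dropout allowance no longer keeps power above 80%.

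The completion count raises a similar problem. The number completing is the plan's measure of tolerability, so the expected figure should agree with the number randomized.

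**Working it through.** **Inputs** (Sample Size Calculation, SDs confirmed by Table 1): difference d = 5.1; SD 6.4 for drug and 5.3 for placebo; two-sided alpha 0.05; Welch t-test.

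**Formulas.** v1 = SD1²/n1 and v2 = SD2²/n2. SE = √(v1 + v2). Satterthwaite df = (v1 + v2)² / [v1²/(n1 − 1) + v2²/(n2 − 1)]. Noncentrality = d/SE. Power is the probability that a noncentral t variable with that df and noncentrality falls outside ± the 97.5% point of t.

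**Step 1: the plan's 36/15 figure, SDs as stated.**
- v1 = 40.96/36 = 1.138; v2 = 28.09/15 = 1.873
- SE = √3.010 = 1.735; df = 31.5; critical t = 2.038
- Noncentrality = 5.1/1.735 = 2.939
- Power = 81.3%, as printed. The method therefore reproduces one of the plan's own figures.

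**Step 2: the plan's 38/19 figure, SDs as stated.**
- v1 = 40.96/38 = 1.078; v2 = 28.09/19 = 1.478
- SE = √2.556 = 1.599; df = 42.8; critical t = 2.017
- Noncentrality = 5.1/1.599 = 3.190
- Power = 87.6%, against 82.7% printed: a gap of 4.9 points.

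Simulation (400,000 trials per design) gave 87.6% at 38/19 and 81.2% at 36/15.

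**Step 3: the SDs exchanged between arms.**

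| Split (drug/placebo) | SDs as stated | SDs exchanged | Printed |
|---|---|---|---|
| 38/19 | 87.6% | 82.7% | 82.7% |
| 36/15 | 81.3% | 74.0% | 81.3% |

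At 38/19 with the SDs exchanged, SE = √(28.09/38 + 40.96/19) = 1.701, df = 30.7 and noncentrality = 2.997. Exchanging the group sizes instead of the SDs is the same calculation. Each printed figure matches one column, and neither column matches both.

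**Step 4: other explanations tried at 38/19.** Pooled equal-variance t-test, 83.7% (but 75.9% at 36/15, and not the named test); common SD of 6.4, 79.6%; one-sided test, 93.2%; alpha 0.025, 80.3%; normal approximation, 89.1%. None of them reproduces both printed figures.

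**Step 5: power lost with six dropouts.**
- As printed: 82.7 − 81.3 = 1.4 points.
- With the stated inputs, at 36/15: 87.6 − 81.3 = 6.3 points.
- With the stated inputs, at a proportional 34/17: power 83.7%, a loss of 0.8764 − 0.8365, or 4.0 points.
- The split matters: 51 patients give 85.1% if all six losses are on drug (32/19) and 77.7% if all six are on placebo (38/13).

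**Step 6: origin of 5.1.** Table 1's change column gives 2.2 − (−2.8) = 5.0. Its baseline and 12-month means give (142.3 − 140.1) − (136.6 − 139.5) = 2.2 + 2.9 = 5.1. With 5.0, power is 86.4% at 38/19 and 79.8% at 36/15.

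**Step 7: counts.**
- 43/57 = 75.4%. Since 0.80 × 57 = 45.6, more than 80% needs 46 subjects (46/57 = 80.7%).
- 6/57 = 10.5%, whereas 6/51 = 11.8%, so the stated 12% dropout fits only a base of 51.

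**The case against.** The strongest reply is that nothing in the trial depends on this. The corrected power at 57 is higher than the printed one, and both exceed 80%. The 51-patient figure, which carries the dropout allowance, is already right for the stated inputs. The plan can also add patients up to 63; at 42/21 the stated inputs give 90.7%. All of this stands, and it is why the point is a correction to the text and not a challenge to the trial's size. The option to add patients applies only when dropout is higher than anticipated, so it does not remove the misstatement.

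On completion, the plan names no denominator, and 43 is more than 80% of any number up to 53 (43/51 = 84.3%). That is fair, and stating the denominator would be an acceptable remedy. But 51 is the number left after dropout, so it is not a natural base for a completion rate. The natural base is the 57 randomized.

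The 5.0 versus 5.1 difference is rounding within Table 1, and the 12% is a loose percentage. Both are side remarks.

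Finally, the documents do not show how 82.7% arose. An exchange of SDs or group sizes is an inference from an exact match. The inconsistency does not depend on it.

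**Conclusion.** The concern holds. With the plan's stated difference, SDs, alpha and test, power at 38/19 is 87.6%, not 82.7%, while the neighbouring 81.3% at 36/15 is correct. The two printed figures cannot both come from the stated inputs, and Table 1 supports the SDs as written. The calculation assumes normally distributed changes, as the plan's own power analysis does.

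The error understates power, so 57 patients are not too few under the stated assumptions. Its practical effect is to understate the power lost with six dropouts. The exception would be if the exchanged SDs were intended: the 51-patient power would then be 74.0%, below 80%.

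The completion figure is also inconsistent on its natural reading: 43 is 75.4% of the 57 randomized, and it implies 14 non-completers where the dropout allowance assumes 6.

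**What to change.** In the Sample Size Calculation:

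- Replace 82.7% with 87.6% for 57 patients (38/19). Keep 81.3% for 51 patients at 36/15, and add 83.7% for a proportional 34/17.
- If the exchanged SDs were intended, say so, reconcile them with Table 1, and change the 36/15 power to 74.0%.
- State that 5.1 comes from Table 1's baseline and 12-month means. If the change column's 5.0 is preferred, use 86.4% and 79.8%.
- Give the dropout allowance as 6 of 57 (10.5%), or say that 12% is relative to 51.

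In Assessments for Safety, change 43 to 46 subjects, or change the percentage to 75% if 43 is meant, or state the denominator to which 43 refers.

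The cost is wording only. Enrolment, allocation, test and alpha stay as they are.
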